#### 4.4 Sample size calculation

This sample size calculation is conservatively based on the ability to detect at least a moderate effect of Cohen's  $d = .50$  on the primary outcomes at follow-up (T3). A power analysis was conducted with G\*power. The analysis was conducted with a moderate effect size of 0.5, a  $\beta$ -power of .8, a p-value of 5%, and an independent two-sided t-test as method of analysis. This analysis showed that 64 patients need to be included in each condition. This means that a total of 128 patients needs to be included. Accounting for a drop-out of 20%, the goal for inclusion is set at a total of 154 patients. It is important to note that participants in the experimental condition are considered as a 'drop-out' when they don't fill out the questionnaires at all measuring moments, not when they stop using the intervention. In other words: patients can stop using the intervention. In other words: patients can stop using the intervention, but can still complete their participation in the study if they fill out all questionnaires. Adherence to the intervention is not the same as drop-out from the study, since it is a different concept. The main reason for this is that earlier research has shown that patients often stop using these interventions before all lessons are completed, so it is not realistic to expect that all patients fully complete the intervention. In order to account for this, the number of completed lessons will be included as a moderator for effectiveness in the analyses to investigate whether adherence is related to effectiveness. Additionally, a sub-goal of this study is to determine whether engagement is a predictor of adherence and effectiveness to incorporate non-adherence to the intervention in the study. The intended 154 patients will be included at four different organizations that all have multiple forensic outpatient clinics.

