## 8. METHODS

### 8.1 Study parameters/endpoints

In this study, multiple types of data are collected to answer the six research questions. First, a short overview will be provided, after which the specific measurement instruments will be explained in more detail.

The variables for the first research objective – focused on the improvement in regulatory emotional self-efficacy, treatment readiness and aggression – will be collected via short, validated self-report questionnaires that will be administered via Qualtrics. To answer the first research question, three primary outcome measures will be used. The main reason for selecting three outcome measures, is that this is the first RCT on internet-based interventions in forensic outpatient care [16]. Consequently, there are no other RCTs on which the choice for outcome measures can be based. The three main outcome measures are based on qualitative research, combined with insights of therapists and researchers [17, 19, 21, 42]. However, based on these sources, it is not clear which of these outcome measures is best to identify change on the short and long term due to the intervention. The intervention is viewed as potentially effective if the experimental group improves more than the control group on at least one of the outcome measures on T1, T2, and/or T3. The intervention is viewed as effective in case of changes on all three outcome measures on T3.

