## 10. STATISTICAL ANALYSIS

### 10.1 Primary study parameter(s)

Data will be analysed using IBM SPSS software (version 24.0) and significance was accepted at 0.05 or lower. Analyses will be done on intention to treat (ITT) basis.

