#### ***Research objective 1: Self-efficacy, treatment readiness, and aggression***

To identify whether there are changes in dependent variables between the experimental and control group on baseline (T0), during the intervention (T1), post-intervention (T2) and follow-up assessment (T3), multilevel repeated-measures linear mixed models will be used. This analysis method accounts for autocorrelation within participants and missing data. Time and group will be used as fixed factors, along with their interactions, and participants are modelled as random factor. Interaction effects will be studied to identify whether the changes over time differed between groups. Main effects for time will be used to investigate whether the scores of all participants changed over time. In order to provide more insight into the main findings, Least-significant difference (LSD) post-hoc independent t-tests with Bonferroni correction will be performed to test for significant between-group differences and changes over time per group.

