#### ***Determining effectiveness***

In order to determine whether the internet-based intervention Aggression is effective, multiple scenarios are possible.

First of all, it is possible that the scores of the experimental groups do not increase more than those of the control group on all three primary outcome measures at all measurement points (T1, T2 and T3). In that case, the intervention is viewed as ineffective. Second, there might be a significant improvement of the experimental group compared to the control group on one or more of the outcome measures on T1 (so halfway the intervention), but not on T2 and T3. This indicates that the intervention shows some promise, but cannot be viewed as effective. Further research on why the effects are not maintained until the end of the intervention and on the long term is then warranted. These questions will be partly answered by means of the interviews at T3. Third, there might be a change on T2 - so directly after completing the intervention - on one or more of the outcome measures in the experimental group compared to the control group, which is not maintained at T3. In that case, the intervention is viewed as promising and potentially useful for clinical practice because participants did experience benefits, but not effective because the effects are not maintained on the long term. In that case, future research into why these effects are not maintained and what this means for the usefulness of these interventions in forensic outpatient care is necessary. Fourth, there might be an improvement of the experimental group compared to

the control group on T3 on one or two outcome measures. In that case, the intervention is viewed as effective since it leads to benefits on the long term. However, future research is again warranted to investigate why these changes did not occur on the other outcome measure(s). Finally, if the experimental group outperforms the control group on all three outcome measures at T3, the conclusion will be that the intervention is effective and no future research is warranted. However, this of course does not mean that future research is not desirable for the sake of replicability.

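### Section 10.1 tests within-patient change with independent t-tests and applies Bonferroni to no stated family, and no section names the test or alpha behind the T3 effectiveness verdict

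*Combined protocol and SAP*

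**What the plan says.** Section 10.1, Research objective 1, specifies a linear mixed model for each outcome: "Time and group will be used as fixed factors, along with their interactions, and participants are modelled as random factor". Its leading comparison is the interaction: "Interaction effects will be studied to identify whether the changes over time differed between groups". To shed further light on the main results it adds: "Least-significant difference (LSD) post-hoc independent t-tests with Bonferroni correction will be performed to test for significant between-group differences and changes over time per group". No number of comparisons is given. The only significance level in section 10.1 is "significance was accepted at 0.05 or lower", without saying whether it applies per test or per family.

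The verdicts come under Determining effectiveness, by visit and outcome. The intervention is ineffective if the experimental group's scores "do not increase more than those of the control group on all three primary outcome measures" at T1, T2 and T3. Gains seen only at T1 or only up to T2 earn weaker labels. If one or two outcomes are better at T3: "In that case, the intervention is viewed as effective since it leads to benefits on the long term". Section 8.1 sets a stricter rule: "The intervention is viewed as effective in case of changes on all three outcome measures on T3".

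The sections also disagree on which outcomes are primary. Section 8.1 counts three. In section 8.1.1, the RESE text presents emotional self-efficacy as the primary outcome, and the AVL-AV text says aggression was not chosen as primary and is secondary.

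Section 4.4 sizes the trial at T3 for d = 0.5 and 80% power with "a p-value of 5%, and an independent two-sided t-test as method of analysis". It arrives at 64 per arm and a recruitment target of 154 to allow for 20% drop-out.

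**The concern.** Three things are left wrong or open.

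- **Within-group change.** These are repeated scores from the same patients. An independent t-test ignores their correlation.
- **Correction.** Bonferroni has no meaning until the family is stated. If each outcome at each visit is its own family, there is one comparison and alpha stays at 0.05. If the family is three outcomes, alpha is 0.05/3. If it is three outcomes by three visits, alpha is 0.05/9.
- **Deciding test.** A four-visit interaction does not isolate T3, and no T3 contrast is named. The only test tied to T3 is the t-test in section 4.4, which is named for sizing.

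Two analysts could follow the plan faithfully, use different tests and alphas at T3, and reach different verdicts from the same data. The power in section 4.4 belongs to just one of the possible combinations. If the choice is made after the data are seen, it can follow the results.

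**Working it through.** **Inputs.** From section 4.4: d = 0.5, two-sided 0.05, 64 per arm, 154 recruited, 20% drop-out. After drop-out, 154 × 0.8 = 123.2, about 61.5 per arm. Not in the documents, so assumed: T0-T3 correlation r of 0.4 / 0.5 / 0.6, between-outcome correlation of 0 to 0.5, equal SD at every visit, complete data.

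**1. The plan's own figure.** Two-sample t-test with noncentrality d × √(n/2). At n = 64 this is 0.5 × √32 = 2.83, and power at two-sided 0.05 is 80.1%. The 64 per arm reproduces.

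**2. The same test with a Bonferroni family of k**, alpha = 0.05/k:

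| n per arm | k = 1 | k = 3 | k = 9 |
|---|---|---|---|
| 64 | 80.1% | 65.6% | 50.5% |
| 61.5 | 78.5% | 63.5% | 48.2% |

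**3. Other candidates for the T3 test, 61.5 per arm.** The raw t-test has SE √(2/61.5) = 0.180 SD. The planned model's group difference at T3, with a free mean for each group at each visit, has the same SE. The T3-T0 interaction contrast multiplies it by √(2(1−r)). A contrast adjusted for T0 multiplies it by √(1−r²).

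| r | Interaction SE | Power at 0.05 | Power at 0.05/3 | T0-adjusted SE | Power at 0.05 | Power at 0.05/3 |
|---|---|---|---|---|---|---|
| 0.4 | 0.198 | 71% | 54% | 0.165 | 85% | 72% |
| 0.5 | 0.180 | 79% | 64% | 0.156 | 89% | 78% |
| 0.6 | 0.161 | 87% | 75% | 0.144 | 93% | 85% |

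The interaction contrast at 0.05/3 reaches 80% at r of about 0.64, and 87% at r = 0.7.

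**4. Independent test on paired data.** The independent SE is proportional to √2 and the paired SE to √(2(1−r)). The ratio is 1/√(1−r) = 1.29 / 1.41 / 1.58. With r above zero the test is too conservative. At r = 0.5 its true size is 2 × P(Z > 1.96 × 1.41), about 0.6% instead of 5%.

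**5. No correction, one of three outcomes sufficient at T3, no true effect.**
- Any significant result, independent outcomes: 1 − 0.95³ = 14.3%. At between-outcome correlation 0.5 (simulated): 12.5%.
- A significant result in favour of the intervention, independent outcomes: 1 − 0.975³ = 7.3%. At correlation 0.5 (simulated): 6.3%.

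The second pair is the chance of a false effective verdict, because the verdict requires improvement. The comparator for a single two-sided 0.05 test is 2.5%.

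**The case against.** The best defence is that the plan has a hierarchy. The mixed model and its interaction come first, the t-tests are there for added insight, and the verdict wording about not increasing more than control fits an interaction contrast. That is fair, and it confines the paired-data error to supporting analyses. It does not supply the T3 contrast or its alpha.

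A reader might infer four stronger things that the documents do not support.

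- **That LSD and Bonferroni flatly contradict each other.** The phrase can be read as ordinary pairwise tests with their threshold then corrected. The wording is loose. The real gap is the missing family.
- **That the 80% holds only if nothing is corrected.** This is true of section 4.4's t-test. It is not true in general: the planned T3-T0 contrast can reach 80% at 0.05/3 when r is about 0.64 or more, and can miss it uncorrected (71% at r = 0.4).
- **That the family has three outcomes.** Section 8.1 says so, but the RESE and AVL-AV texts in section 8.1.1 do not agree. The 0.05/3, 0.05/9 and one-of-three figures are conditional on three.
- **That a false effective verdict has a chance of 12.5% to 14.3%.** Those figures count significant results in either direction.

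It is also fair to say that the planned model's handling of baseline is not shown to be an error.

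**Conclusion.** The point stands in a limited form. The independent t-test for within-group change is wrong as written, though conservative and without bearing on the T3 verdict. The Bonferroni family is undefined, and neither the test nor the alpha for the T3 verdict is named.

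Section 4.4's 80% is correct for the calculation it reports. On that test at 64 per arm it drops to 66% or 50% with a family of three or nine (64% or 48% at 61.5 per arm). For a model contrast, power may fall on either side of 80%, with or without correction, depending on r. With three primary outcomes, one sufficing and no correction, the false-effective risk is 6.3% to 7.3% against 2.5%. That excess comes from the one-outcome-suffices rule combined with the missing family. These sizes rest on the assumed correlations and on complete data.

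**What to change.** 1. Replace the post-hoc t-test sentence with contrasts from the mixed model: group differences at T1, T2 and T3, and within-group changes.
2. Name the T3 contrast as the deciding test for each primary outcome. The planned T3-T0 interaction contrast is the minimum. Adjusting for T0 is preferable, through a common T0 mean in both arms or, for the group differences, T0 as a covariate. This changes the planned model. It is a cheap gain in precision (SE 0.156 against 0.180 at r = 0.5) and not the correction of an error.
3. Reconcile section 8.1 (three primary outcomes, all needed) with Determining effectiveness (one or two suffice) and with the RESE and AVL-AV texts in section 8.1.1.
4. State one alpha rule over the resulting primary outcomes: Holm at an overall 0.05 if any one suffices, each at 0.05 if all are required, no correction if there is only one.
5. State that the T1 and T2 contrasts are supportive, and give the threshold behind the labels of some promise and promising.
6. Restate the power in section 4.4 for the chosen test and rule.

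The cost is wording, a revised model specification and a new power statement, with no new data. The stated power may fall below 80%. With three outcomes under Holm and only one truly changing, T0-adjusted power at 0.05/3 is 72% / 78% / 85% at r = 0.4 / 0.5 / 0.6. If all three are required and d = 0.5 holds on each, simulated joint power at 61 and 62 per arm is about 48-59% for the raw t-test and 62-69% / 70-76% / 81-84% adjusted for T0, over between-outcome correlations of 0 to 0.5. The rule should be fixed before any T3 data are analysed.

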#### ***Determining effectiveness***

In order to determine whether the internet-based intervention Aggression is effective, multiple scenarios are possible.

First of all, it is possible that the scores of the experimental groups do not increase more than those of the control group on all three primary outcome measures at all measurement points (T1, T2 and T3). In that case, the intervention is viewed as ineffective. Second, there might be a significant improvement of the experimental group compared to the control group on one or more of the outcome measures on T1 (so halfway the intervention), but not on T2 and T3. This indicates that the intervention shows some promise, but cannot be viewed as effective. Further research on why the effects are not maintained until the end of the intervention and on the long term is then warranted. These questions will be partly answered by means of the interviews at T3. Third, there might be a change on T2 - so directly after completing the intervention - on one or more of the outcome measures in the experimental group compared to the control group, which is not maintained at T3. In that case, the intervention is viewed as promising and potentially useful for clinical practice because participants did experience benefits, but not effective because the effects are not maintained on the long term. In that case, future research into why these effects are not maintained and what this means for the usefulness of these interventions in forensic outpatient care is necessary. Fourth, there might be an improvement of the experimental group compared to

the control group on T3 on one or two outcome measures. In that case, the intervention is viewed as effective since it leads to benefits on the long term. However, future research is again warranted to investigate why these changes did not occur on the other outcome measure(s). Finally, if the experimental group outperforms the control group on all three outcome measures at T3, the conclusion will be that the intervention is effective and no future research is warranted. However, this of course does not mean that future research is not desirable for the sake of replicability.

When interpreting the results and answering the first research questions, nuance will be added by investigating when and how long changes within and between groups take place. This will not just be done by post hoc analyses and visualizations of data, but also by means of qualitative research with patients and therapists, i.e. the interviews that will take place at T3. By means of these interviews, more insight will be gained into why changes are or are not observed, whether the selected outcome measures were suitable, if and how the intervention can cause changes on the short and long term, and whether it is of added value for clinical practice.

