It is clear that there is a pressing need for research into if, why and for whom internet-based interventions work. Qualitative research has highlighted several potential benefits of internet-based interventions that require further research [19, 21]. These outcomes were mostly related to aggression regulation, since this is an important and large part of outpatient treatment. In general, therapists did see multiple advantages, but indicated that they did not expect any major improvements due to these interventions: they were mostly expected to slightly bolster the effectiveness of existing treatment, mostly by providing patients with more tools to work on their treatment independently. Because of this, changes might be attributed to the patient's own effort as opposed to that of the therapist, which could benefit **self-efficacy** towards behaviour change. Additionally, internet-based interventions offer multiple ways of acquiring knowledge and skills that are tailored to the target group, such as multi-media, written assignments and peer-stories. This is done to accommodate different types of learning that better fit the patient than face-to-face treatment sessions and can thus also increase the patient's confidence in regulating their aggression. Furthermore, therapists also expected that these intervention can positively affect **treatment readiness** of patients because they can support the patient in gaining insight into their problems and defining their own goals. Being responsible for their own treatment by working on an internet-based intervention individually, and gaining more insight into their own behaviour, might influence their sense of ownership and motivation to work on their treatment. Therapists, patients and researchers expect that this potential increase in self-efficacy and treatment readiness could facilitate actual behaviour change: **aggression** might decrease due to the independence, knowledge, insights and skills that are acquired by means of these interventions [17]. This can result in decreased risk for recidivism, reflected in an improved score on **risk assessment instruments**. Finally, it is also expect that, if used well, these

interventions might result in more **efficient treatment** because part of face-to-face treatment can be replaced by the internet-based intervention [21, 27]. However, for all of these expectations goes that they are based on qualitative research.

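### The effectiveness rule in section 10.1 is inconsistent on direction for aggression, and it can return an effective verdict at T3 while aggression is significantly worse

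*Combined protocol and SAP*

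**What the plan says.** The verdict rule appears in two places in the combined protocol and SAP.

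**Section 10.1, Determining effectiveness**, sets out five scenarios:

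- First: ineffective when "the scores of the experimental groups do not increase more than those of the control group on all three primary outcome measures", at T1, T2 and T3.
- Second: some promise, but not effective, when "there might be a significant improvement of the experimental group compared to the control group on one or more of the outcome measures on T1" but not later.
- Third: promising when "there might be a change on T2 - so directly after completing the intervention - on one or more of the outcome measures", if this is not maintained at T3.
- Fourth: improvement relative to "the control group on T3 on one or two outcome measures. In that case, the intervention is viewed as effective". Of the remaining measures it says only that "future research is again warranted to investigate why these changes did not occur on the other outcome measure(s").
- Fifth: effective when the experimental group outperforms control on all three measures at T3.

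**Section 8.1** gives a shorter version: potentially effective if the experimental group improves more on at least one measure at any of T1 to T3. It then says: "The intervention is viewed as effective in case of changes on all three outcome measures on T3".

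On direction, section 1 expects that aggression "might decrease due to the independence, knowledge, insights and skills that are acquired by means of these interventions", and section 8.1.1 expects self-efficacy to rise more than under TAU. Section 2 sets the objective as more improvement in all three. No section states the scoring direction of the AVL-AV or defines improvement per instrument.

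**The concern.** There are two separate problems.

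1. **Direction.** The first scenario is phrased for scales on which higher is better. That suits RESE and CVTRQ. It does not suit aggression, where benefit is a fall. The scenarios also use three kinds of wording: a rise, an improvement, and an undirected change.
2. **Worsening.** No scenario attaches a verdict to the experimental group doing significantly worse on a measure. The fourth scenario treats the remaining measures as though the only possibility were that nothing happened. The planned tests can detect worsening: the sample size rests on a two-sided test, and between-group differences are tested post hoc. The verdict ignores what they find.

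The label matters because section 11.4.1 expects the result to influence implementation, and section 4.1 gives prevention of (re)offending as the main goal of this care. An effective verdict beside significantly more self-reported aggression would mislead the clinics it is meant for.

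**Working it through.** **Inputs.** Section 4.4: d = 0.5, power 0.80, two-sided alpha 5%, 64 per condition. Section 10.1: significance at 0.05, and the five scenarios. Assumed here: a higher AVL-AV score means more aggression; normal test statistics; a correlation of 0 to 0.5 between outcomes on the benefit scale.

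**The plan's own figure.** Normal approximation: n = 2 × (1.960 + 0.842)² / 0.5² = 62.8, so 63. The exact t-test gives 63.77, so 64, with power 0.801. The stated 64 is reproduced.

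**Chance that one measure is significant.** The standardised effect is 0.5 / √(2/64) = 0.5 / 0.1768 = 2.828. The chance of significance in the true direction is Φ(2.828 − 1.960) = Φ(0.868) = 0.807. For a measure with no effect, the chance of significance in one given direction is 0.025.

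**Wording side by side.**

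| Place | Term used | Does a fall in aggression count as benefit? |
|---|---|---|
| 10.1, first scenario | increase | Not as written |
| 10.1, second and fourth | improvement | Yes |
| 10.1, third | change; benefit implied by the sentence that follows | Implied |
| 10.1, fifth | outperforms | Yes |
| 8.1, potentially effective | improves more | Yes |
| 8.1, effective | changes | Implied by the sentence before it |

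**Case A: only aggression changes, falling by d = 0.5, judged at T3.** The first scenario is read as no measure rising significantly more than control.

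- Literal first scenario (ineffective): 0.975² = 0.951.
- At least one improvement (effective): 1 − (1 − 0.807) × 0.975² = 0.817.
- Both at once: 0.951 × 0.807 = 0.767.

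These figures assume independent outcomes. Simulation (400,000 runs) over correlations 0 to 0.5 gives about 95%, 81% and 76–77%. The first scenario also covers T1 and T2. If all six RESE and CVTRQ tests were independent, its probability would be 0.975⁶ = 0.859 and the overlap 0.859 × 0.807 = 0.69.

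**Case B: RESE improves by d = 0.5, aggression rises by d = 0.5, no effect on CVTRQ.**

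- Effective under the fourth scenario: 1 − (1 − 0.807) × 0.975 = 0.812.
- Effective together with a significant rise in aggression: 0.812 × 0.807 = 0.655.
- Simulation for the joint event: 0.657, 0.635 and 0.622 at correlations 0, 0.3 and 0.5, so 62–66%.

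**Case C: RESE and CVTRQ both improve by 0.5 and aggression rises by 0.5.** Independent: (1 − 0.193²) × 0.807 = 0.963 × 0.807 = 0.777. Simulation: 73–78%.

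**Effect of the Bonferroni correction.** Section 10.1 plans one but does not give the number of comparisons. For Case B with independent outcomes:

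- Three comparisons: critical value 2.394, Φ(0.434) = 0.668. Joint: [1 − 0.332 × (1 − 0.0083)] × 0.668 = 0.45.
- Nine comparisons: critical value 2.773, Φ(0.055) = 0.522. Joint: [1 − 0.478 × (1 − 0.0028)] × 0.522 = 0.27.

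The exact t-test gives single-test power of about 0.66 and 0.50 in place of 0.668 and 0.522.

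**The case against.** The best defence is that the intended direction is clear. Section 2, section 8.1 and three of the five scenarios speak of improvement or outperformance, and section 1 says aggression should fall. On that view the word in the first scenario is a drafting slip. That is probably right, and it limits the direction problem to an inconsistency.

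Two stronger readings are tempting, and the documents do not support them.

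- *The rule demands that all three scores rise.* The first scenario applies when scores do not rise more. Since later scenarios credit one or more measures, it most naturally means on none of the three, although not on all three is also a possible reading.
- *A fall in aggression counts against the intervention.* Even literally, the first scenario only fails to credit a fall, and the fourth scenario would call the same result effective.

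On worsening, the defence has four points. Section 8.1 would give only potentially effective in Case B. The fifth scenario already excludes worsening. Section 10.1 promises nuanced interpretation with post hoc analyses and interviews. Opposite effects of d = 0.5 also run against the mechanism in section 1, where greater self-efficacy helps to reduce aggression. All of this is correct. But 8.1 and 10.1 conflict, and 10.1 is the detailed analysis rule. Unspecified nuance after results are known changes no verdict.

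Section 8.1.1 also calls aggression a secondary outcome. That does not help, because 8.1 and 10.1 both count it among three primary measures in the rule. Whether worsening should cancel or merely qualify a favourable verdict is the sponsor's choice, but the choice has to be written down beforehand.

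**Conclusion.** The point holds in two parts of unequal weight.

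The direction wording is an internal inconsistency. If AVL-AV scores rise with aggression, a trial in which only aggression falls by d = 0.5 satisfies two opposite verdicts at T3 in about 76–77% of cases, unadjusted.

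The missing rule for worsening is the part that matters, and correcting the direction word does not close it. Followed as written, the fourth scenario labels an aggression intervention effective even when aggression is significantly worse than control. The size, 62–66% in Case B, illustrates how little the rule protects against that outcome; it is not a forecast. It rests on assumed opposite effects of d = 0.5, 64 analysed per arm, unadjusted 5% tests and correlations of 0 to 0.5. With Bonferroni over three to nine comparisons it falls to about 0.45 to 0.27 for independent outcomes.

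A reader might infer that the trial would call a harmful intervention effective about 80% of the time. That figure is only the power of a single test. Nothing in the documents suggests that harm on aggression is expected.

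**What to change.** Amend sections 8.1 and 10.1 before any outcome data are examined by arm:

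1. State the benefit direction of each instrument: RESE and CVTRQ higher than control, AVL-AV lower than control, with the AVL-AV scoring direction given.
2. Replace the rise in the first scenario, and the undirected change in the third scenario and in 8.1, with improvement in the stated direction. In the first scenario, say that it applies when none of the three measures improves.
3. Reconcile 8.1 with 10.1 on how many measures at T3 an effective verdict needs.
4. Add to the second, third and fourth scenarios: if any primary measure is significantly worse than control at that time point, the result is reported as mixed or possible harm, not as promising or effective. The fifth scenario needs no such condition.

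This needs no new data or patients. The cost is a slightly harder favourable verdict. If one measure truly improves by d = 0.5 and the other two are unaffected, a chance worsening would remove the effective label in about 0.807 × (1 − 0.975²) = 0.04 of trials when outcomes are independent, and in about 0.02 at correlation 0.5 (simulation, unadjusted).
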